## DOCUMENT HISTORY

VERSION	DATE	DESCRIPTION
Version 1.0	29-SEP-2022	Initial Release
Version 2.0	09-NOV-2022	Revision to include the waiving of informed consent for this study.
Version 3.0	11-NOV-2022	Update to Section 1.1 Schedule of Activities.
Version 4.0	18-NOV-2022	Update to obtain participant informed consent per request from IRB review.

MED-2022-DIV60-002

18-NOV-2022

Version 4.0

**CONFIDENTIAL**

# 1. PROTOCOL SUMMARY

## 1.1. Synopsis

**Title:**

Wet Time for a Foam Hand Sanitizer with 70% ethyl alcohol

**Study Description:**

Hand sanitizers are a standard of hygiene requirements. They must be effective at reducing germ count on the hands while ideally providing emollients to moisturize the skin after use. Spectrum™ Advanced Hand Sanitizer Foam (70%) (hereby referred to as Spectrum Advanced Foam) kills over 99.99% of germs within 15 seconds while boasting double digit increases in hand moisture after two weeks of use.

In 2002 and 2009 the Center for Disease Control and Prevention (CDC) and World Health Organization (WHO) published guidance that hands should remain wet for at least 15 seconds while being rubbed together after application of an alcohol-based hand rub, though the recommendations do not specify the volume of product to be apply.

This study will evaluate the “wet time” of Spectrum Advanced Foam, which will be defined as the length of time in which the sanitizer foam stays wet on the hands while the participant rubs their hands with the foam sanitizer. The participant will first be asked to wash and dry their hands. Participants will review the appropriate hand sanitizer application steps, as detailed by the WHO guidance. Then, a 1.0 mL or 1.4 mL\* aliquot of Spectrum Advanced Foam will be dispensed from an automated dispenser to the participant’s hands. The participant will be asked to rub their hands together following the WHO method for hand sanitizer application until they declare the product has dried sufficiently for the donning of medical gloves. Study personnel will measure the wet time of Spectrum Advanced foam using a stopwatch.

**Phase:**

Post-market.

---

\* The study is to include an interim analysis of the data after 46 participants have completed the study on the medium dispenser setting (1.0 mL). If the results demonstrate a satisfactory 15 second wet time using the medium setting, the study will end and no further recruitment will take place. If at this point, the results demonstrate that the amount of hand sanitizer dispensed under the medium setting (1.0 mL) does not sufficiently stay wet for at least 15 seconds, a second data collection will take place with another 46 participants who will undergo the study using the high dispenser setting (1.4 mL).

Primary Objective:	To determine the duration of time during which a 1.0 mL or 1.4 mL* aliquot of Spectrum Advanced Hand Sanitizer Foam remains wet under conventional use conditions.
Primary Endpoint:	The time during which 1.0 mL or 1.4 mL* of Spectrum Advanced Hand Sanitizer Foam remains wet under conventional use conditions.
Study Population:	
Number of participants, N = 46.
 
Inclusion criteria
 
Individuals who meet the following criteria will participate in this study:
 
 
➤ Individual <math>\geq</math> 18 years of age.
 
 
Exclusion criteria
 
Individuals who meet any of the following criteria will not be allowed to participate in this study:
 
 
➤ Individual has a self reported skin condition that might result in irritation from the hand sanitizer.
 
➤ Individual has a known allergy to the ingredients in the test product.
 

Power Analysis Methods:	The sample size of 46 was estimated for 95% confidence interval based on a standard deviation of 5 seconds and target distance from mean to limits of 1.5 seconds (PASS-Confidence Intervals for One Mean). Results from a previous study conducted by Ecolab (summarized in the Appendix) was utilized as a starting point for sample size estimation for the current protocol, using PASS 2021 Power Analysis and Sample Size Software (2021). NCSS, LLC. Kaysville, Utah, USA, ncss.com/software/pass .
Description of Sites/Facilities Enrolling Participants:	
The study will be conducted at private rooms within the Northfield location of Medline Industries, LP.
 
Address: [name]

---

\* The study is to include an interim analysis of the data after 46 participants have completed the study on the medium dispenser setting (1.0 mL). If the results demonstrate a satisfactory 15 second wet time using the medium setting, the study will end and no further recruitment will take place. If at this point, the results demonstrate that the amount of hand sanitizer dispensed under the medium setting (1.0 mL) does not sufficiently stay wet for at least 15 seconds, a second data collection will take place with another 46 participants who will undergo the study using the high dispenser setting (1.4 mL).

[name]

**Description of Study Design:**

Informed consent will be obtained from participants in-person or remotely. Participants will then undergo in-person or remote screening, after which participants who meet inclusion criteria will be enrolled in this prospective study. The participant will first be asked to wash and dry their hands, and wait an additional two minutes after drying their hands. Participants will review the steps for applying hand sanitizer, adapted from the WHO guidance. The participant will then be asked to apply an aliquot of Spectrum Advanced Foam, dispensed from an automatic dispenser (X10 Dispenser, Medline Industries, LP), to their hands. The participant will be instructed to rub their hands together with the sanitizer until their hands are dry. Study staff will measure and record the wet time of Spectrum Advanced Foam.

**Participant Duration:** Approximately 30 minutes.

## 1.1. Schedule of Activities (SOA)

Required Study Activities and Assessments	Visit 1
Verification of Eligibility	X
Participant Washes and Dries Hands	X
Participant Waits 2 Minutes	X
Participant Reviews Hand Sanitizer Application Steps (Adapted from WHO)	X
1.0 mL or 1.4 mL * Aliquot of Spectrum Advanced Foam Applied to Palm	X
Study Staff Starts Timer	X
Participant Rubs Hands and Fingers Until Participant Declares to Study Staff that Hands and Fingers are Dry for Donning of Gloves	X
Study Staff Stops Timer	X
Wet Time Measurement	X
Participant Dismissal	X
Adverse Events	X

\*The study is to include an interim analysis of the data after 46 participants have completed the study on the medium dispenser setting (1.0 mL). If the results demonstrate a satisfactory 15 second wet time using the medium setting, the study will end and no further recruitment will take place. If at this point, the results demonstrate that the amount of hand sanitizer dispensed under the medium setting (1.0 mL) does not sufficiently stay wet for at least 15 seconds, a

*second data collection will take place with another 46 participants who will undergo the study using the high dispenser setting (1.4 mL).*

## **2. INTRODUCTION**

### **2.1. Background & Rationale**

Hand sanitizers are a standard of hygiene requirements. They must be effective at reducing germ count on the hands while ideally providing emollients to moisturize the skin after use. In 2002 and 2009 the CDC and WHO published guidances that hands should remain wet for at least 15 seconds while being rubbed together after application of an alcohol-based hand rub, though the recommendations do not specify the volume of product to be apply.

The CDC specifically recommends applying alcohol-based hand sanitizers by applying the manufacturer-recommended amount of sanitizer directly to the palm of one hand and then rubbing the hands together. The sanitizer must entirely cover the surfaces of both hands and all fingers while rubbing the hands together until the product has dried.

The goal of this study is to evaluate the “wet time” of Spectrum Advanced Foam, which will be defined in this study as the length of time in which the foam sanitizer stays wet on the hands while the participant rubs their hands with the foam sanitizer.

### **2.2. Study Products**

#### **2.2.1. Medline Spectrum™ Advanced Hand Sanitizer Foam (70%)**

Spectrum Advanced Hand Sanitizer Foam kills over 99.99% of germs within 15 seconds. The formula includes added moisturizers to help reduce dry skin. The SKU number for Medline Spectrum Advanced Hand Sanitizer Foam is HH70F1000H.

### **2.3. Risk/Benefit Profile**

#### **2.3.1. Potential Study Risks**

This study entails minimal risk to the participants. Spectrum Advanced Foam is commercially available and widely used in clinical settings. There is the possibility of minor skin irritation with the application of Spectrum Advanced Foam, however the magnitude of this should be no greater than what occurs through the normal use of the hand sanitizers. In addition, the study is designed such that the test product will be applied on the non-compromised skin of participants with no self-reported known skin conditions, which should impose less risk for study participants.

#### **2.3.2. Potential Study Benefits**

Direct benefit to the study participants is unlikely. However, the results from this study will provide the wet time for Spectrum Advanced Foam, which may better inform product efficacy and infection prevention for individuals applying Spectrum Advanced Foam to the hands.

### 2.3.3. Assessment of Potential Risk/Benefit Profile

As this study entails minimal risk to the study participants and the results may further inform the wet time of Spectrum Advanced Foam, the risk/benefit profile of this study is acceptable.

## 3. OBJECTIVES AND ENDPOINTS

OBJECTIVES	ENDPOINTS	JUSTIFICATION FOR ENDPOINT(S)
Primary		
1. To determine the duration of time during which a 1.0 mL or 1.4 mL* aliquot of Spectrum Advanced Hand Sanitizer Foam remains wet under conventional use conditions.	1. The time during which 1.0 mL or 1.4 mL* of Spectrum Advanced Hand Sanitizer Foam remains wet under conventional use conditions.	1. To evaluate if the wet time of the Spectrum Advanced Hand Sanitizer Foam meets CDC guidance of a minimum 15 seconds wet time.

*\*The study is to include an interim analysis of the data after 46 participants have completed the study on the medium dispenser setting (1.0 mL). If at this point, the results demonstrate that the amount of hand sanitizer dispensed under the medium setting (1.0 mL) does not sufficiently stay wet for at least 15 seconds, a second data collection whereby another 46 participants will undergo the study using the high dispenser setting (1.4 mL) will take place. If the results demonstrate a satisfactory 15 second wet time using the medium setting (1.0 mL) with 46 participants, the study will end and no further recruitment will take place.*

## 4. STUDY DESIGN

### 4.1. Overall Design

This will be a prospective study that will be conducted over the course of one study visit. This study will measure the “wet time” of Spectrum Advanced Foam to evaluate if Spectrum Advanced Foam meets the CDC and WHO guidance that hands should remain wet for at least 15 seconds while being rubbed together after application of an alcohol-based hand rub. “Wet time” will be defined as the length of time in which the sanitizer foam stays wet on the hands while the participant rubs their hands with the foam sanitizer.

Informed consent will be obtained either in-person or remotely. Following in-person or remote remote participant screening, the participant will be asked to wash and dry their hands and wait an additional two minutes. The participants will review the steps for hand sanitizer application, adapted from a WHO poster on application of handrubs. The participants will be instructed to apply a 1.0 mL or 1.4 mL\* aliquot of Spectrum Advanced Foam to their hands. The Spectrum Advanced foam will be dispensed from an automated dispenser. The participant will then be asked to rub their hands together with the foam sanitizer until their hands are dry, following the WHO recommended method for hand sanitizer application. Study staff will use a stopwatch to measure the wet time: the application of the product to the palm of the participant will indicate the “start time”, and the participant stating that their hands have dried will indicate the “stop time”.

After the participant has indicated that their hands have dried sufficiently for the donning of gloves, study staff will record the wet time of Spectrum Advanced Foam. The participant will then be dismissed from the study.

#### **4.2. End of Study Definition**

A participant will have completed their study participation when all study activities are completed at the end of Visit 1.

This study will be considered complete upon issuance of a Clinical Study Report that has been approved by the Clinical Affairs Director.

### **5. STUDY POPULATION**

#### **5.1. Inclusion Criteria**

Individuals who meet the following criteria will participate in this study:

- Individual  $\geq$  18 years of age.

---

\* The study is to include an interim analysis of the data after 46 participants have completed the study on the medium dispenser setting (1.0 mL). If the results demonstrate a satisfactory 15 second wet time using the medium setting, the study will end and no further recruitment will take place. If at this point, the results demonstrate that the amount of hand sanitizer dispensed under the medium setting (1.0 mL) does not sufficiently stay wet for at least 15 seconds, a

*second data collection will take place with another 46 participants who will undergo the study using the high dispenser setting (1.4 mL).*

## **5.2. Exclusion Criteria**

Individuals who meet any of the following criteria will not be allowed to participate in this study:

- Individual has a self reported skin condition that might result in irritation from the hand sanitizer.
- Individual has a known allergy to the ingredients in the test product.

## **5.3. Strategies for Recruitment and Retention**

Participants will be recruited from an internal database of Medline employees. Participants will have previously participated in studies conducted by Medline, and/or have agreed to be contacted for future studies, as well as possibly via IRB-approved advertisement(s). Potential participants will be screened and enrolled until a total of 46 participants with complete data are obtained. Participants that do not complete study activities will be withdrawn from the study and replaced to meet the desired N = 46.

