**Figure 1. Hand Sanitizer Application Steps (Adapted from the WHO “How to Handrub?” Poster)**

The participants will then be instructed by study staff to apply a 1.0 mL or 1.4 mL\* aliquot of Spectrum Advanced Foam to their hands, which will be provided from an automated dispenser, following the hand sanitizer application steps. Study staff will begin to measure the wet time using a calibrated stopwatch: the application of the product to the palm of the participant will indicate the “start time”, and the participant stating that their hands have dried will indicate the “stop time”.

Once the participant has indicated that their hands are dry enough to don medical gloves, study staff will stop the stopwatch and record the Spectrum Advanced Foam wet time in the CRF.

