#### **9.5.2. Secondary Endpoint**

None.

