#### iii. Data Handling and Record Keeping

Data collection is the responsibility of the study staff at the site under the supervision of the PI. The PI is responsible for ensuring the accuracy, completeness, legibility, and timeliness of the data reported in the CRFs or any other study activity documentation as

part of this study. All the documents should be completed in accordance with Good Documentation Practices (GDP) to ensure accurate interpretation of data.

Final storage of Medline data will be per ICH/GCP guidelines and kept stored in a protected access area for the length of the time required.

iv. Conflict of Interest Policy

The independence of this study from any actual or perceived influence is critical. Therefore, any actual conflict of interest of persons who have a role in the design, conduct, analysis, publication, or any aspect of this trial will be disclosed and managed.

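### The participant's own statement stops the only endpoint, participants can all be sponsor employees, and the visible procedures do not keep the stopwatch or the 15 s target from them

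*Combined protocol and SAP*

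**What the plan says.** - **Endpoint.** Wet time is the single primary endpoint (section 9.5.1), and section 9.5.2 lists no secondary endpoint.
- **Stop event.** In sections 4.1 and 6.1.2, "the participant stating that their hands have dried will indicate the" stop time. The Schedule of Activities has: "Participant Rubs Hands and Fingers Until Participant Declares to Study Staff that Hands and Fingers are Dry for Donning of Gloves". No observer-based or objective dryness check is described. Sections 4.1 and 6.1.2 word the stop event both as hands having dried and as hands dry enough for gloves.
- **Timing.** Section 6.1.2: "Study staff will begin to measure the wet time using a calibrated stopwatch". The text does not say whether the participant can see the stopwatch or hear elapsed time.
- **Participants.** Section 5.3: "Participants will be recruited from an internal database of Medline employees". Advertisements are mentioned as a possibility, with no minimum share of non-employees. Section 5.2 has two exclusions: a self-reported skin condition, and "Individual has a known allergy to the ingredients in the test product". Neither concerns a person's job.
- **Decision.** There is no randomization (section 9.2) and no comparator. Sections 8 and 9.8 judge the 1.0 mL result against an average of 15 s, and a shortfall leads to a second cohort of 46 at 1.4 mL.
- **Independence.** Section 10.a.iv: "The independence of this study from any actual or perceived influence is critical". It then provides that conflicts of people with a role in the trial are disclosed and managed.

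**The concern.** The person who ends the measurement may work for the product's manufacturer, and could work on this product or on the study itself. If that person knows the target or can see the timer, the declaration of dryness can move without any intent.

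In a controlled comparison, a shift common to both arms would largely cancel. Here it passes in full into the one mean that is compared with 15 s. The planned 95% interval measures sampling error only, and a larger sample would narrow it around the shifted value. The shift could not be examined afterwards either: sections 6.1.1.2 and 9.6 record age, sex and hand size, but not job role or knowledge of the target.

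Two things are at stake: the estimated duration, which is the stated objective, and the decision whether 1.0 mL meets the 15 s guidance or a second cohort is needed.

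**Working it through.** **Inputs.** SD 5 s, n = 46, target half-width 1.5 s, 95% confidence (section 9.1). Threshold: a mean of 15 s (sections 8 and 9.8). The only planning mean in the documents is 17.1 s, from 42 subjects using 0.7 mL of a different foam (Appendix b). The documents give no size for a reporting shift, so every shift b below is an assumption.

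**The plan's own figure.** The smallest n with t(0.975, n−1) × 5/√n ≤ 1.5:
- n = 45: 2.015 × 5/√45 = 1.502 s, too wide.
- n = 46: 2.014 × 5/√46 = 1.485 s, which meets the target.

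The stated 46 is reproduced, and this point does not affect it.

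**Effect on the decision.** SE = 5/√46 = 0.737 s. With true mean m and shared delay b, taking a pass as a sample mean of at least 15 s:

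P(pass) = Φ((m + b − 15)/0.737)

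For example, with m = 14 and b = 0, the argument is −1/0.737 = −1.357, giving 8.7%. With b = 1 it is 0, giving 50%.

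| True mean | b = 0 | b = 0.5 s | b = 1 s | b = 2 s |
|---|---|---|---|---|
| 13 s | 0.3% | 2.1% | 8.7% | 50% |
| 14 s | 8.7% | 24.9% | 50% | 91.3% |
| 14.5 s | 24.9% | 50% | 75.1% | 97.9% |

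At m = 17.1 s with no shift, 2.1/0.737 = 2.85, giving 99.8%. A delay has almost nothing left to change.

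The formula is symmetric. A participant group that declares 1 s early at a true mean of 15.5 s would move the chance from 75.1% to 24.9%.

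**A stricter reading of a pass.** The plan does not require the lower 95% limit to exceed 15 s. If it did (noncentral t, 45 df), a 1 s delay would move the chance from 0.1% to 2.5% at 14 s, and from 0.4% to 9.7% at 14.5 s.

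**Effect on the estimate.** Coverage of the true mean by the 95% interval depends only on the shift, not on where the true mean lies: 95% with no shift, 89.8% with 0.5 s, 73.6% with 1 s, 48.8% with 1.5 s and 24.4% with 2 s.

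**The case against.** Several counter-arguments have force.

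- **Self-declaration suits the endpoint.** The aim is wet time in conventional use, ending when the user judges the hands ready for gloves. The earlier study in Appendix b also stopped when the subject said the hands felt dry. This stands, and self-declaration should be kept. It does not explain leaving the stopwatch and target unaddressed.
- **Direction is not shown.** A reader might infer that the bias must run towards a pass. The documents do not support that. A participant might stop early, since readiness for gloves may come before full dryness, or might regard quick drying as a merit. A reader might also infer a stronger bias in a second cohort recruited after a shortfall, but nothing shows this, and that cohort may never be recruited.
- **What participants are told is unknown.** The consent form and the content of Figure 1 are not in the public text, and the screening form and CRF are separate documents. No section says that participants learn the target or see the timer. The point is therefore limited to a safeguard missing from the visible procedures.
- **The size depends on the true mean.** The move from 24.9% to 75.1% is symmetric about 15 s and is the largest swing that a 1 s delay can produce. It should not be read as typical.
- **Employees are not the only source.** Advertisements may be used, so the sample can be, but need not be, all employees. The conflict policy also extends to any aspect of the trial, which may reach study-team members who enrol. It still names no measure for the participants who generate the endpoint.

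**Conclusion.** The point holds as a gap in safeguards, not as evidence of bias. The sole endpoint ends on the participant's word, all participants can be sponsor employees, including people who work on the product or the study, and the visible procedures do not shield the stopwatch, elapsed time or 15 s target. Towards a pass is the most plausible direction, because that is where knowledge of the target would pull, but neither direction nor size is established.

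Under the protocol's SD and sample size, a shift below the planned 1.5 s half-width could reverse the decision if the true mean is near 15 s. The effect of a 1 s delay is small at 13 s and negligible at 17.1 s. That last figure belongs to another product and volume, so it cannot be relied on here. Bias in the estimated duration would remain wherever the true mean lies. The change is worth making because it is cheap and the problem cannot be corrected after data collection.

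**What to change.** Keep the participant's declaration as the stop event, and make these changes:

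1. **Section 6.1.2:** require that the stopwatch is out of the participant's sight, that elapsed time is not spoken, and that staff use a script giving the purpose neutrally (how long the foam takes to dry), without the 15 s target. Check that the consent form and Figure 1 are consistent with this.
2. **Section 5.2:** exclude study-team members and employees who work on the hand-hygiene product line.
3. **Sections 8 and 6.1.2:** state that participants in any second cohort are not told the first cohort's result.

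The cost is protocol wording, a short script, IRB review of both, and a somewhat smaller employee pool, whose size the documents do not give. No extra participants, visits or staff are needed. The sample could still consist entirely of sponsor employees, so the report should say how many were.
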